12.12. Follow-up Visit Month 12 (365 \pm 30 days)

The 12-month follow-up office visit (365 \pm 30 days) will include the following assessments:

- 24-Hour Ambulatory BP Monitoring
- Limited physical exam including height and weight
- Quality of Life Assessment
- Blood assays (serum creatinine, CBC and platelets, BMP and HbA1c)
- Office-based sitting and standing blood pressure and heart rate
- Medications administered since last visit
- Adverse events

12.13. Follow-up Visit Month 18 (540 \pm 30 days)

The Month 18 follow-up office visit (540 \pm 30 days) will include the following assessments:

- Limited physical exam including height and weight
- Office-based sitting and standing blood pressure and heart rate
- Medications administered since last visit
- Adverse events

12.14. Follow-up Visit Month 24 (730 \pm 30 days)

The 24-month follow-up office visit (730 \pm 30 days) will include the following assessments:

- Limited physical exam including height and weight
- Quality of Life Assessment

- Blood assays (serum creatinine, CBC and platelets, BMP and HbA1c)
- Office-based sitting and standing blood pressure and heart rate
- Medications administered since last visit
- Renal Duplex Ultrasound (DUS) - for subjects who received renal denervation treatment and reached the 24-month follow-up visit following approval of protocol version AH:
 - Subjects will be required to have duplex ultrasound to assess for evidence of significant stenosis, defined as $\geq 60\%$ as reported by the duplex ultrasound (DUS) core laboratory. A significant stenosis ($\geq 60\%$) detected by DUS will trigger the performance of a confirmatory CTA or DSA.
 - If a diagnostic duplex ultrasound cannot be adequately achieved at the 24-month follow-up, then a CTA or DSA must be conducted.
- Adverse events

12.15. Follow-up Visit Month 30 (900 \pm 30 days) [Visit/Assessments Not Required After Approval of Protocol vAH]

The 30-month follow-up office visit (900 \pm 30 days) will include the following assessments:

- Limited physical exam including height and weight
- Office-based sitting and standing blood pressure and heart rate
- Medications administered since last visit
- Adverse events

12.16. Follow-up Visit Month 36 (1095 \pm 30 days) [Visit/Assessments Not Required After Approval of Protocol vAH]

The 36-month follow-up office visit (1095 \pm 30 days) will include the following assessments:

- Limited physical exam including height and weight
- Quality of Life Assessment
- Blood assays (serum creatinine, CBC and platelets, BMP and HbA1c)
- Office-based sitting and standing blood pressure and heart rate
- Medications administered since last visit
- Adverse events

12.17. Study Completion

All subjects, independent of group to which they were randomized will be followed through a minimum of 24 months post randomization. BSC will notify the study sites when the follow-up period has ended for all subjects.

12.18. Source Documents

Table 12.18-1 includes, but is not limited to, a summary of source document requirements. Where copies of the original source document as well as printouts of original electronic source documents are retained, these shall be signed and dated by a member of the investigation center team with a statement that it is a true reproduction of the original source document. Data documented in the eCRF relevant to device deficiencies, relationship of AE to study device(s), may be considered source data for the study.

Table 12.18-1: Source Documentation Requirements

Requirement	Disposition
Written Informed Consent	Retain at study site
24-hour Ambulatory BP Monitor Report	Retain at study site
Medical visit information (vital signs, medication administration, physical exam, etc.) gathered in the clinic/hospital	Retain at study site
Laboratory Test Results and Calculated eGFR	Retain at study site
Renal Duplex Ultrasound (DUS) report	Retain at Core Laboratory
Angiography Reports for Digital Subtraction Angiography (DSA) and Computed Tomographic Angiography (CTA)	Retain at Core Laboratory
Renin and Aldosterone Test Results	Retain at Core Laboratory

Abbreviations: BP=Blood Pressure; eGFR=Estimated Glomerular Filtration Rate

13. Medication Additions

13.1. Rescue Medications

Subjects will remain off antihypertensive medications through the primary efficacy assessment (8 weeks post randomization) unless rescue changes are required. Rescue medications will be introduced if a subject's OSBP is ≥ 180 mmHg at two consecutive visits. The OBP recheck visit must occur within 3 days of the initial elevated reading. The recheck OBP should be measured according to the methodology described in Section 12.1.1.1. If rescue medications are required, the investigator should initiate therapy immediately with appropriate agents (typically a 2-drug antihypertensive combination) and it is also

recommended that the Investigator consults with the Study HTN Coordinating Principal Investigator.

NOTE: Investigators have ultimate discretion regarding the type of antihypertensive medication and timing of adding rescue medications to ensure subject safety.

13.2. Medications for Subjects Not at Target

If subjects are not at target from the time of the primary efficacy assessment (8 weeks post randomization) through the 6-month assessment, antihypertensive medications will be added and doses escalated. Target blood pressure is defined as OSBP <140 mmHg.

Note: At the 8 week follow up time point, the investigator may use ABPM data, along with OSBP data, to determine the need for anti-hypertensive medications.

Medications and dose escalation must continue until target BP is reached and throughout the 6-month follow-up period. After anti-hypertension medications are introduced and a subject reaches target, no additional medication additions or adjustments should be made prior to the 6-month follow-up assessment other than for rescue of excessively high blood pressures or for symptomatic hypotension.

The recommended medication addition and adjustment protocol is described in Figure 13.2-1. The type and dose of antihypertensive medication is based on Investigator discretion. The recommended algorithm is suggested through the 6-month follow-up visit.

[figure not shown]

Figure 13.2-1 Addition of Medications Algorithm

13.3. Medication Adjustment Visits

Subjects requiring medication additions or adjustments will require a follow-up visit 2 weeks after the antihypertensive drug has been introduced or the dose modified. Investigators must obtain OBP according to the details in Section 12.1.1.1 during the 2-week follow-up visit. Two-week follow-up visits and medication additions/adjustments should continue until blood pressure reaches target.

14. Statistical Considerations

14.1. Endpoints

14.1.1. Primary Efficacy Assessment

Due to enrollment termination with approximately half of the planned subjects randomized, the primary efficacy assessment will be observational only. No formal tests of hypotheses will be performed.

The primary efficacy assessment for the study is mean reduction in average 24-hour ASBP through 8 weeks post randomization in subjects treated with renal denervation (Test) and subjects treated with masked procedure (Control).

14.2. General Statistical Methods

14.2.1. Analysis Sets

The primary and pre-specified additional assessments will be analyzed on an intent-to-treat (ITT) basis and on a per-protocol basis. For the ITT analysis, all subjects who sign the written ICF and are randomized in the study will be included in the analysis population, regardless of whether the subjects receive the assigned treatment. For the per-protocol analysis, only randomized subjects who meet the eligibility criteria and receive the assigned treatment will be included in the analysis population.

The ITT population will be the primary analysis set for the purpose of assessing superiority of Test to Control for 8-week average 24-hour ASBP reduction. All other endpoint analyses will be based on ITT population.

14.2.2. Randomization Scheme

Randomization to treatment will be stratified by study site. A computer generated list of random treatment allocations (i.e., a randomization schedule) will be used to assign subjects to treatments in a 2:1 ratio of Test to Control. This list will be specific to the subject's site. Random permuted blocks of varying sizes will be employed to ensure approximate balance of treatment allocation within each site.

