Test Device	Vessix Renal Denervation System: 
 • Vessix Reduce™ Catheter (4.0, 5.0, 6.0 and 7.0 mm) • Vessix™ Generator (bipolar radio frequency)
Control Therapy	Masked procedure (renal angiogram)
Device Sizes	The Vessix Reduce Catheter is available in balloon diameters of 4.0 mm, 5.0 mm, 6.0 mm and 7.0 mm with a balloon length of 25 mm and a total catheter working length of approximately 90 cm. The number of electrodes on each balloon varies from 4 to 6 bipolar electrodes, depending on balloon diameter. The catheter is compatible with a 7F guide sheath.
Study Design	Prospective, multicenter, single blinded, randomized, controlled, pilot study
Planned Number of Subjects	Up to 100 randomized subjects
Planned Number of Centers / Countries	Up to 20 centers in the US
Primary Efficacy Assessment	Mean reduction in average 24-hour ambulatory systolic blood pressure (ASBP) at 8 weeks post randomization Due to enrollment termination (51 subjects randomized), the primary efficacy statistical hypothesis testing will not be conducted. All assessments will be observational.
Safety Assessments	Safety Assessments analyzed at all follow-up time points: 
 • All-cause death • Renal failure • Hospitalization for hypertensive crisis • Hospitalization due to severe hypotension/syncope

REDUCE-HTN: REINFORCE	
	
Safety Assessments analyzed at 4 weeks:
 
 • Significant embolic event resulting in end-organ damage or intervention to prevent it • Renal artery dissection or perforation requiring intervention • Vascular complications requiring surgical repair, interventional procedure, thrombin injection, or blood transfusion 
Safety Assessments analyzed at 6 months:
 
 • Significant new renal artery stenosis assessed by duplex ultrasound (DUS) and confirmed by the angiographic core laboratory [$>70\%$ stenosis by computed tomographic angiography (CTA) or digital subtraction angiography (DSA)] through 6 months post randomization 
Note: All Safety Assessments will be adjudicated by an independent Clinical Events Committee (CEC).

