14.2.4. Number of Subjects per Study Site

Study sites will not be allowed to randomize more than 10 subjects without prior approval from the Sponsor (10% of the total number of randomized subjects). No center will be allowed to enroll more than 20 subjects (20% of the total number of randomized subjects).

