14.3. Data Analyses

Baseline data will be summarized by treatment group for the randomized study. Subject demographics, clinical history, procedure assessment, and medication compliance will be summarized using descriptive statistics (e.g., mean, standard deviation, n, minimum, maximum) for continuous variables and frequency tables for discrete variables. The analysis unit may be (but will not be limited to) by subject, catheter, or treatment.

Test and Control in the randomized study will be compared as needed with a Chi-square test or a Fisher exact test for discrete variables and a Student t-Test for continuous variables. The differences between Test and Control in the randomized study and their 95% confidence intervals will be presented as needed.

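### The between-arm comparisons in 14.3 ignore the site stratification, so the 95% interval for continuous outcomes is somewhat too wide if sites differ materially (minor)

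*Combined protocol and SAP*

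**What the plan says.** Section 14.2.2 sets the allocation. "Randomization to treatment will be stratified by study site", from a list specific to each site that is used to "assign subjects to treatments in a 2:1 ratio of Test to Control". It adds: "Random permuted blocks of varying sizes will be employed to ensure approximate balance of treatment allocation within each site". The block sizes are not given.

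Section 14.3 names the between-arm methods: chi-square or Fisher exact for discrete variables and "a Student t-Test for continuous variables", with differences and 95% intervals shown where useful. None of these has a site term, and no other section of the document puts site into a between-arm analysis.

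The synopsis gives the scale: "Up to 20 centers in the US", and "Due to enrollment termination (51 subjects randomized), the primary efficacy statistical hypothesis testing will not be conducted". Section 14.1.1 makes the primary assessment observational. Sections 14.3.2 and 14.3.5 refer to a separate Statistical Analysis Plan, whose analysis text is not in the document.

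**The concern.** The analysis should reflect how subjects were randomized. When Test and Control are balanced within each site, a site whose subjects all do better or worse shifts both arms together, and most of that shift cancels from the difference. A pooled t-test does not know this. It counts the between-site spread as noise, so its standard error exceeds the true sampling error.

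With formal testing withdrawn, the difference and its interval are the main between-arm information left to read. At 51 subjects that interval is already wide, so precision already secured by the design is worth keeping. What is at stake is precision only.

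**Working it through.** The plan states no power, detectable difference or interval width, so it has no figure of its own to reproduce.

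**Inputs from the documents.** 51 subjects randomized 2:1, so about 34 Test and 17 Control; up to 20 sites; at most 20 subjects per site (14.2.4). The SD of the 24-hour systolic change is 14.4 mmHg, from the 6-month result of the sponsor's earlier single-arm study (5.2.1). That SD sets the mmHg scale only; ratios and coverage do not depend on it.

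**Assumptions.** Site ICC from 0 to 0.3; 10, 15 or 20 enrolling sites of uneven size; blocks of 3 and 6, or 3, 6 and 9; all 51 subjects analysed; no treatment-by-site interaction.

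**Step 1: the nominal t interval.** SE = 14.4 × √(1/34 + 1/17) = 14.4 × 0.2970 = 4.28 mmHg. With 49 degrees of freedom t = 2.01, so the half-width is 8.6 mmHg and the full width 17.2 mmHg.

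**Step 2: the most that site can matter.** With exact 2:1 balance in every site, only the within-site variance, (1 − ICC) × SD², remains in the true sampling error. The t interval would then be too wide by a factor of about 1/√(1 − ICC).

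**Step 3: realistic balance.** Sites average between 51/20 = 2.6 and 51/10 = 5.1 subjects, so many blocks stay incomplete and the ceiling is not reached. Simulation (4,000 trials per setting) compared the reported t width with the width that the estimator's empirical SD requires:

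| Assumed ICC | Ceiling 1/√(1 − ICC) | Reported ÷ needed width | Coverage of t interval |
|---|---|---|---|
| 0.05 | 1.03 | 0.99–1.02 | 94.8–95.6% |
| 0.10 | 1.05 | 1.01–1.06 | 95.2–96.6% |
| 0.20 | 1.12 | 1.03–1.08 | 95.3–96.4% |
| 0.30 | 1.20 | 1.06–1.12 | 96.3–97.1% |

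Ranges run over site counts and block mixes. Monte Carlo error is about 2% on the ratio and 0.7 points on coverage. A separate simulation with blocks of 3 or 6 gave 10–13% excess at ICC 0.3, and the planned 100 subjects would give 11–15% there. Hence the overall statement of about 6–15% at 0.3.

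**Step 4: fixed site effects.** Mean 95% interval width in mmHg, fixed-site model against t-test:

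| Assumed ICC | 10 sites | 20 sites |
|---|---|---|
| 0.05 | 17.3–17.5 vs 17.1 | 19.4–19.7 vs 17.2 |
| 0.10 | 16.9–17.0 vs 17.1 | 18.9–19.3 vs 17.1–17.2 |
| 0.20 | 15.9–16.1 vs 16.9 | 17.7–18.2 vs 17.1–17.2 |
| 0.30 | 14.9–15.0 vs 16.8–16.9 | 16.7–16.9 vs 17.1 |

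With 20 sites this model spends 19 degrees of freedom, and single-arm sites contribute nothing to the difference. It is wider than the t-test until the ICC is about 0.3.

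**Step 5: a random site intercept.** With a Kenward-Roger-type adjustment (two runs of 1,500 per setting, 10, 15 and 20 sites), the interval was narrower than the t interval by about 1% at ICC 0, 2% at 0.05, 3–4% at 0.1, 6–8% at 0.2 and 10–13% at 0.3. Coverage was 93.5–95.7%. On a 17.2 mmHg interval, 6–8% is 1.0–1.4 mmHg of full width (0.06 × 17.2 and 0.08 × 17.2). The empirical SD of the estimate itself improved by only 0–4%.

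**The case against.** The strongest reply is that the loss may be nil. No ICC is documented. The primary outcome is a change within subject, so stable site differences in pressure level cancel. Section 12.1.1.2 has the core laboratory supply the equipment and manage the data, which should limit site effects further. Nothing in the documents supports an ICC of 0.2 or 0.3, and at 0.05 or less the t interval is close to nominal. This stands, and it is why the point is minor.

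Second, the mixed model mostly changes the reported standard error rather than the estimate, and it can err the other way when site variance is small. In one simulation using 49 degrees of freedom without the Kenward-Roger correction, the worst setting (10 sites, ICC 0.1) covered 93.1% against 94.7% for the t-test. With the correction the lowest value was 93.5%. This is a real but small cost.

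Third, the analysis is descriptive and a late change of model may look data-driven. That argues for documenting the change before analysis. It does not justify leaving the mismatch in place.

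Two stronger readings are tempting. A reader might infer that the t-test is the only planned comparison. It is not: 14.3 also names chi-square and Fisher tests, all are to be used where needed, and the separate Statistical Analysis Plan may already adjust for site. A reader might also infer that the interval is too wide whenever sites differ. At an ICC of 0.05 sites do differ, yet the excess cannot be told from zero.

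**Conclusion.** The mismatch is real: the design stratifies by site, and the comparisons named in 14.3 do not use site. The consequence for continuous outcomes is an interval that is somewhat too wide if sites differ materially. The amount depends on an assumed ICC, and also on assumed block sizes, number of enrolling sites and site sizes.

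The documents do not support reading this as bias in the estimated difference or as a risk of a false efficacy claim. The error runs in the conservative direction and no formal test remains. Low priority, but cheap to put right.

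**What to change.** In 14.3, for between-arm differences in continuous outcomes, including the 8-week change in 24-hour ambulatory systolic pressure, replace the Student t-test with a linear mixed model: treatment plus a random intercept for the randomizing site, fitted by REML with Kenward-Roger degrees of freedom. Report the difference and its 95% interval from that model. It reduces to the t-test when the estimated site variance is zero. Do not use fixed site effects.

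Leave the discrete comparisons as they are. With strata averaging about 2.6 to 5.1 subjects, a site-stratified risk difference would need single-arm sites to be pooled after allocation is known, and no calculation supports that step.

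The cost is one sentence in 14.3 and a few lines of SAS, with no new data. Section 14.3.5 requires an amended Statistical Analysis Plan approved before the analysis is run. Coverage may sit near 94% when site variance is small. If the separate plan already adjusts for site, only 14.3 needs to be aligned with it.

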14.2.3. Control of Systematic Error/Bias

Selection of subjects will be made from the Investigators' general or professional referral population. All subjects meeting the inclusion/exclusion criteria and having signed the ICF will be eligible to enroll in the study. Consecutively eligible subjects should be enrolled into the study to minimize selection bias. Study subjects will be randomly assigned to a treatment group within the investigational site. In determining subject eligibility for the study, the investigator's assessment of imaging will be used. However, the Angiographic Core Laboratory will independently analyze the angiograms for all renal denervation procedures and the data obtained from the core laboratory will be used for analyses in order to control

for inter-observer variability. An independent CEC composed of medical experts will adjudicate safety assessments, as defined in the CEC Charter.

14.2.4. Number of Subjects per Study Site

Study sites will not be allowed to randomize more than 10 subjects without prior approval from the Sponsor (10% of the total number of randomized subjects). No center will be allowed to enroll more than 20 subjects (20% of the total number of randomized subjects).

14.3. Data Analyses

Baseline data will be summarized by treatment group for the randomized study. Subject demographics, clinical history, procedure assessment, and medication compliance will be summarized using descriptive statistics (e.g., mean, standard deviation, n, minimum, maximum) for continuous variables and frequency tables for discrete variables. The analysis unit may be (but will not be limited to) by subject, catheter, or treatment.

Test and Control in the randomized study will be compared as needed with a Chi-square test or a Fisher exact test for discrete variables and a Student t-Test for continuous variables. The differences between Test and Control in the randomized study and their 95% confidence intervals will be presented as needed.

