All subjects will be followed at 2 weeks and 1, 3, 6, 12, 18 and 24 months. Follow-up assessments will include office blood pressure measurement, blood assays and urinalysis for renal function, renal DUS at 6 months, and ambulatory blood pressure monitoring (ABPM) at 6 and 12-months. Subjects are required to maintain compliance with all antihypertensive medications throughout the follow-up period.

At 6 months, the mean office SBP was 157.5 ± 23.5 mmHg, a reduction of 24.7 ± 22.1 mmHg compared with baseline ($P < .0001$), thus met the efficacy primary endpoint for the study. Twenty four-hour ambulatory SBP was reduced by 8.4 ± 14.4 mmHg at 6 months ($P < .0001$). No pre-specified acute safety events occurred. However, one subject (0.7%) was hospitalized for a hypertensive emergency unrelated to medication and/or non-compliance within 1 month of the procedure. One subject (0.7%) had renal artery stenosis which required an intervention. Three other subjects had flow-limiting stenosis in the renal artery at 6 months which did not require intervention. ¹⁴

Subject follow-up in the REDUCE-HTN Study continues and data monitoring activities are ongoing through 2 years post procedure.

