After the primary endpoint was met, 46 control patients (cross over group) underwent renal denervation. Esler et al¹⁷ [ENREF 18](#) reported that the 6-month follow up of the cross over group showed a significant drop in blood pressure (190.0/99.9 mmHg to 166.3/91.5 mmHg). The one-year follow-up of the initial RDN group continued to show significantly lower blood pressure when compared to baseline office BP; although BP at 12 months was slightly elevated from the 6-month average (-31.7/-11.7 at 6 months compared to -28.1/-9.7 at 12 months).

As with HTN-1, a favorable safety profile was observed in HTN-2. Safety outcomes for HTN-2 demonstrated no serious procedure or device related complications or elevated occurrence rates of adverse events. In the treatment group, one subject had a possible progression of an underlying atherosclerotic lesion but required no further treatment.

The Simplicity HTN-3¹⁸ trial is a pivotal study designed as a prospective, randomized, masked procedure, single-blind trial evaluating the safety and effectiveness of catheter-based bilateral renal denervation for the treatment of resistant hypertension despite compliance with at least 3 antihypertensive medications of different classes at maximal tolerable doses. Bhatt et al¹⁹ report 535 patients were enrolled into the trial; 2 treatment : 1 control (masked procedure). The primary efficacy endpoint of mean change at 6 months in systolic office blood pressure was not met. The reduction for the treatment group was -14.13±23.93 mmHg and for the control was -11.74±25.94 mmHg; P=0.26. The study continued to demonstrate safety of the technology with a 1.4% major adverse event rate for the renal denervation group and 0.6% for the masked procedure group. Ongoing discussions continue as to why these results do not replicate those of previous trials. Medication compliance and adjustments are thought to have played a role.²⁰

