9.2.1.2. Control

The control for the primary efficacy assessment is a masked procedure.

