10.2. Inclusion Criteria

Subjects who meet all of the following criteria (see Table 10.2-1) may be given consideration for inclusion in this clinical investigation, provided no exclusion criterion (see Section 10.3) is met.

Table 10.2-1: Inclusion Criteria

- | |
|---|
| 
• Age ≥ 18 and ≤ 75 years• OSBP ≥ 150 mmHg and ≤ 180 mmHg based on an average of 3 office-based blood pressure measurements• Average 24-hour ASBP ≥ 135 mmHg and ≤ 170 mmHg• For each kidney, a main renal artery, with or without accessory renal arteries, with diameter ≥ 3.0 mm and ≤ 7.0 mm and length ≥ 20.0 mm• Agrees to have all study procedures performed, and is competent and willing to provide written, informed consent |
|---|

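### The week-8 Test-minus-Control difference in 24-hour ASBP is not committed to as the reported estimate, and the only method named for it is an unadjusted t-test (minor)

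*Combined protocol and SAP*

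**What the plan says.** Section 14.1.1 makes the primary assessment observational: "No formal tests of hypotheses will be performed". It then describes the quantity of interest as the mean reduction in average 24-hour ASBP "in subjects treated with renal denervation (Test) and subjects treated with masked procedure (Control"). It names no difference between the arms.

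The between-arm difference with an interval appears only in 14.3: "The differences between Test and Control in the randomized study and their 95% confidence intervals will be presented as needed". The comparisons named there, also left to discretion, are chi-square or "Fisher exact test for discrete variables and a Student t-Test for continuous variables". The supplied text has no baseline covariate and no site term, although 14.2.2 stratifies randomization by site.

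Two other passages point towards a contrast. Section 9.2.1.2 says: "The control for the primary efficacy assessment is a masked procedure". Section 14.2.1 makes ITT the primary set for assessing superiority of Test to Control on 8-week ASBP. Sections 14.3.2 and 14.3.5 refer to a separate Statistical Analysis Plan, which was not supplied.

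**The concern.** Dropping a test does not remove the need for an estimate. In a randomized trial with a masked control, the estimate that uses the design is the difference between arms, and its interval shows how little 51 subjects can settle. As 14.1.1 and 14.3 stand, a report giving only the two within-arm reductions would comply.

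Within-arm reductions are a weaker summary here. Entry requires "Average 24-hour ASBP ≥ 135 mmHg and ≤ 170 mmHg" at screening, and Table 12.1-1 has one combined screening and baseline column, so the reading that selects the subject is also the baseline. Each arm's fall can therefore include regression to the mean, which cancels in expectation only in the difference. The masked-procedure pivotal trial cited in 5.2.1.1 shows how far a control arm can move: "The reduction for the treatment group was -14.13±23.93 mmHg and for the control was -11.74±25.94 mmHg; P=0.26". There the control arm fell by 11.74/14.13 = 83% as much as the treated arm, and the difference was 14.13 - 11.74 = 2.39 mmHg. Those are 6-month office pressures in medicated patients, so they illustrate the issue but do not set its scale here.

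The second part concerns method. An unadjusted comparison of change leaves any chance baseline imbalance in the estimate, and in a trial this small that imbalance can be several mmHg. Baseline ASBP is already collected on every subject.

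**Working it through.** **Plan's own figures.** The current text gives no alpha, power, effect size or SD for the primary comparison, so there is no design figure to reproduce. The one arithmetic check is 51/100 = 51%, which agrees with the statement in 14.1.1 that about half the planned subjects were randomized.

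**Inputs from the documents.** 51 randomized (synopsis); 2:1 allocation (14.2.2); 24-hour entry window 135 to 170 mmHg and office window 150 to 180 mmHg (10.2). The SD of change comes from the sponsor's earlier single-arm study (5.2.1): "Twenty four-hour ambulatory SBP was reduced by 8.4 ± 14.4 mmHg at 6 months". That was at 6 months on medication, so 14.4 is a proxy.

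**Assumed.** A 34:17 split; SD of change also varied from 10 to 16.

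**Step 1: width of the unadjusted interval.** Half-width = t(0.975, 49) × SD × √(1/34 + 1/17) = 2.0096 × SD × 0.2970.
- SD 14.4: 8.60 mmHg (8.38 at 32:19, 8.89 at 36:15)
- SD 10, 12, 16: 5.97, 7.16, 9.55 mmHg

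**Step 2: model for baseline.** None of these values is in the documents. Usual 24-hour ASBP is normal with mean 140, 145 or 150 and SD 13; within-person SD is 6, 8 or 10 per visit. Usual office pressure averages 5 to 15 higher, with SD 15, correlation 0.5 to 0.7 with usual ASBP, and visit SD 8 to 12. A simulated subject is kept if both screening readings fall in the entry windows, and no treatment effect is applied. Among those kept, baseline SD is 8.4 to 9.3 and the slope of change on baseline is -0.19 to -0.46.

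**Step 3: effect of chance imbalance.** A 1-in-20 imbalance is 1.96 × baseline SD × 0.2970, which is 4.9 mmHg at SD 8.4 and 5.4 at SD 9.3. Multiplied by the size of the slope within each scenario, it shifts the unadjusted difference by about 1.0 to 2.5 mmHg. ANCOVA removes this expected shift.

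**Step 4: regression to the mean within an arm.** The expected fall with no treatment effect is -0.3 to 2.7 mmHg. Over 36 scenarios at office visit SD 10 (3 means × 3 within-person SDs × 2 office gaps × 2 correlations) the median is 0.7. A Test-arm 95% interval would then lie wholly on the side of a fall in 2% to 21% of trials, median about 7%, against a nominal 2.5%. About seven in ten scenarios are at or below 10%. The between-arm interval favours Test in 2.2% to 2.8%.

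**Step 5: precision gain from adjustment.** The ratio of residual SD to change SD is √(1 - ρ²), with ρ = slope × baseline SD / change SD. For example, slope 0.41, baseline SD 8.9 and change SD 13.2 give ρ = 0.28 and a ratio of 0.96. Across scenarios, and using either the model's change SD (8.2 to 13.2) or 14.4, the ratio of standard errors is about 0.95 to 1.00, a gain of 0 to 5%.

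The textbook formula √((1 + r)/2) suggests intervals 19%, 13% and 8% narrower at r = 0.3, 0.5 and 0.7. It assumes equal variance at baseline and week 8. With change SD 14.4 it implies a baseline SD of 14.4/√(2(1 - r)) = 12.2, 14.4 and 18.6. A variable confined to a 35 mmHg window cannot have an SD above 17.5, and one spread uniformly over it has 10.1. The smaller gain is therefore the one to quote.

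**The case against.** **The separate SAP may already specify this.** That stands as a limit. The finding concerns the supplied text; if the SAP names the contrast and model, a citation in 14.3 is enough.

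**A contrast is intended.** Section 14.2.1 names superiority of Test to Control on this endpoint, and 14.3 mentions the difference and its interval. A reader might infer from 14.1.1 that no between-arm comparison is planned, or that the sponsor means to report only within-arm falls. The documents do not support that. What is missing is the commitment, and 14.2.1 also sits awkwardly beside the withdrawal of testing.

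**The t-test is valid.** Correct. Under randomization the unadjusted comparison of change is unbiased, and a reader might wrongly take this point to say otherwise. The argument for ANCOVA is removal of chance imbalance at almost no cost. It is not a claim of bias or of a large gain in precision.

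**The regression-to-the-mean figures rest on assumptions.** Also correct. The range includes zero, the median of 0.7 mmHg is small against a half-width of 8.6, and the 21% comes from one corner (mean 140, within-person SD 10, office gap 15, correlation 0.5). It would be wrong to read it as the expected error rate.

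**Little turns on it in a stopped pilot.** Largely true. If each arm's mean, SD and n are given, a reader can rebuild the unadjusted interval, though not the adjusted one. This keeps the point minor.

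**Conclusion.** The point holds as a minor one. The supplied text leaves the primary contrast and its interval to discretion and names only an unadjusted method, while 14.2.1 shows that a comparison is intended. Under the assumed population values, adjustment would remove a shift of about 1.0 to 2.5 mmHg in the event of a 1-in-20 baseline imbalance of about 5 mmHg. Within-arm falls would contain a median of about 0.7 mmHg of regression to the mean (range about -0.3 to 2.7). The unadjusted interval would be about ±8.6 mmHg, assuming a 34:17 split and an SD borrowed from a different population and time point. The documents do not support the stronger conclusions that the t-test is invalid, that within-arm results would be seriously misleading, or that ANCOVA would sharpen the result appreciably.

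**What to change.** 1. In 14.1.1 and 14.3, state that the ITT week-8 Test-minus-Control difference in 24-hour ASBP will be reported with its 95% CI from an ANCOVA adjusted for baseline ASBP. Give the unadjusted difference and CI beside it, and label both as estimates, not tests.
2. State how site, the stratification factor, is handled. With up to 20 sites and 51 subjects, options are a random effect, pooled sites, or omission with a reason.
3. Document the change under 14.3.5 and say whether unblinded week-8 data had been seen. If they had, lead with the unadjusted difference.
4. In 14.2.1, replace the reference to assessing superiority with estimating the Test-minus-Control difference. The comparison should be reworded, not deleted.
5. If the separate SAP already specifies all this, cite it in 14.3 in place of the discretionary wording.

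The cost is wording in three sections, one degree of freedom for baseline ASBP (plus whatever the site choice uses) and one table row. No new data or visits are needed.
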